### **Project summary:**

Policemen recruited in the Chandigarh police who take care of the safety of VIPs most likely suffer from chronic stress, as they need to be vigilant round the clock. Since chronic stress has been shown to be responsible for multiple molecular changes at both the genomic and epigenomic levels, it can lead to various diseases like hypertension, diabetes and even cancer. Further, it has been shown that deregulation in DNA Damage Response (DDR) and DNA repair pathways is responsible for cancer. Though it is well known that yoga relieves stress and anxiety, literature lacks in studies that focus onto assessing the effect of yoga on DDR and DNA repair pathways at the molecular level. In the present study, we propose to investigate the role of yoga in modulating DDR and repair. For this, personnel of Chandigarh police who need to be extra vigilant could be the ideal cohorts. A sample size of around 230 security guards from Chandigarh police shall be recruited in the study with their consent, upon screening them for mild or severe stress on Cohen's Perceived Stress scale. 10 ml of blood will be withdrawn from the participants followed by separation of serum, plasma and WBCs from these subjects. Biochemical assays to measure the levels of cortisol (stress marker) will be performed and analyzed. This study proposes to analyze DDR markers like  $\gamma$ H2AX, 53BP1, and ATM and the extent of damage in WBCs using comet and DNA repair assays. Post the baseline assessments, they will undergo Yoga intervention for a period of 3 months, and at the end of three months, they will be assessed again on the same parameters. The baseline and post intervention results will be compared for discussion and conclusion. This study will help us to understand the effect of yoga in maintaining genomic integrity and stability at the molecular level and can assist the Department of Chandigarh police in designing strategies to improve the overall well being of policemen.

**Key words:** Yoga exercises, DNA damage response (DDR), DNA double-strand break (DSB), DNA double-strand break repair (DSBR), Cancer

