## **Introduction:**

### **Origin of the proposal**

It is well known that yoga relieves stress and anxiety. Since chronic stress has been shown to be responsible for multiple molecular changes at both the genomic and epigenomic levels, that can lead to various diseases like hypertension, diabetes and even cancer. Alterations in DNA damage response (DDR) and repair are considered as one of the major causative agents of cancer. As the effects of yoga on DNA damage response (DDR) and DNA repair are not known, studying the role of yoga will provide us with an insight on the role of yoga in modulating DDR in a way that can alleviate the effects of chronic stress on DDR and repair leading to cancer. DDR is a signaling event, which is activated upon DNA damage and encompasses DNA damage repair, cell-cycle checkpoint activation, apoptosis and senescence. Deregulation in DDR has been known to be responsible for carcinogenesis and it has been suggested that defects in DNA repair is the hallmark of most cancers (Gavande, 2016). Although preliminary studies have reported the effects of yoga in relieving oxidative stress, but no study has investigated the effects of common yoga practice on DDR and DNA repair. This study proposes to analyze the effect of yoga on DDR markers like  $\gamma$ H2AX, 53BP1, and ATM and the extent of damage in WBCs using comet and DNA repair assays. Such analysis will uncover the effect of yoga on DDR and cell survival mechanisms. We will also estimate the extent of oxidative free radicals as well as other DNA repair machinery. We will further evaluate the possible mechanisms by which yoga affects DDR and DNA repair by studying the expression and activation of DDR proteins upon DNA damage. Hence, this study is designed to examine the effect of yoga on DDR and DNA repair and the associated molecular mechanisms. This data could be useful to not only examine the cancer preventive role of yoga but also could be extended to potentiate the therapeutic efficacy of commonly used anti-cancer drugs.

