## **Objectives**

1. Analysis of molecular markers related to DNA damage response and repair before and after the practice of yoga on Chandigarh Police
2. To examine the molecular mechanism by which yoga may modulate DNA damage response and repair.

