### **Design of the study**

In a randomized control trial (RCT), participants are allocated randomly between intervention and control groups to compare the treatments, which enables statistical control over the influences imparted by the aforementioned treatments. In the present study, the policemen who satisfy our eligibility criteria and willing to consent to participate in our study will be enrolled, grouped randomly in intervention and control groups, and assessed for the dependent variables of the study before and after the Integrated Yoga intervention period.

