### **Variables**

- Socio-demographic details – age, diet, alcohol consumption, etc.
- Evaluation of stress level on Cohen's Perceived Stress Scale (pre and post intervention) (Cohen, Kamarck & Mermelstein, 1983)
- Evaluation of stress level using vital parameters: Blood pressure and resting heart rate of participants will be recorded pre and post intervention.

- Evaluation of stress level using molecular parameters: (pre and post intervention) 10 ml of blood will be withdrawn from the subjects by trained phlebotomists, and coded. WBCs and plasma will be separated using standard protocols and stored at -80°C. Plasma will be utilized to assess the levels of cortisol.
- Assessment of chromosomal translocations: (pre and post intervention) Genomic DNA will be extracted from WBCs isolated, and tested for chromosomal translocations using PCR assay. Isolated genomic DNA will be subjected to nested PCR using primers specifically designed to check for t(14;18) and t(11;14) translocations.
- Assessment of DDR and DNA repair:
- *Immunofluorescence*: Isolated PBMCs will be subjected to DDR analysis by immunofluorescence. For this, these cells will be fixed and stained with various DDR markers like γH2AX, 53BP1, pATM.
- *Gene expression analysis*: Total RNA will be isolated from these cells; cDNA will be synthesized and the expression of following DDR and DNA repair genes will be performed using real-time PCR: RAD51, MRE11, RAD50, NBS1, KU70, LIGASE IV, PARP1
- *Comet assay*: Cells will be used to perform both the neutral as well as alkaline comet assay to assess for the number of single- and double-strand breaks.
- Telomeric length: Relative telomere length (TL) using quantitative polymerase chain reaction (qPCR) will be performed on genomic DNA isolated from control and group blood samples and will be compared.

Time Line for experiments:

S.No.	Experiments	Time point
1.	Cortisol levels	0 day
2.	DDR: Immunofluorescence for γH2AX, 53BP1, and ATM.  Gene expression analysis for KU70, LIGASE IV, RAD51,	0 day

	PARP1, MRE11, RAD50, NBS1	
3.	Nested PCR for Chromosomal Translocations	0 day
4.	DNA repair: Comet assay	0 day
5.	Cortisol levels	3 months
6.	DDR: Immunofluorescence for $\gamma$ H2AX, 53BP1, and ATM.  Gene expression analysis for KU70, LIGASE IV, RAD51,  PARP1, MRE11, RAD50, NBS1	3 months
7.	Nested PCR for Chromosomal Translocations	3 months
8.	DNA repair: Comet assay	3 months

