6.1 Comparisons of Two Groups

- **Normally distributed data:** Student's *t*-test (paired or unpaired as appropriate).
- **Non-normal data:** Wilcoxon matched-pairs signed rank test (paired) or Mann-Whitney test (independent).

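### Telomere length is left out of the laboratory Time Line, and its only stated comparison is control versus group, so a before/after result is not secured and baseline precision may go unused

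*Protocol*

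**What the plan says.** The general rule is in the protocol under Design of the study: participants are randomised and "assessed for the dependent variables of the study before and after the Integrated Yoga intervention period". The Project summary says that "at the end of three months, they will be assessed again on the same parameters", without naming telomere length. Objective 1 is "Analysis of molecular markers related to DNA damage response and repair before and after the practice of yoga".

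The Variables section then takes the outcomes one by one. The stress scale, vital signs, cortisol and translocations are each labelled as pre and post. Immunofluorescence, gene expression and the comet assay carry no such label, but each appears in the Time Line for experiments at 0 day and at 3 months. Telomere length has no label and no row. Its entry says that relative length by qPCR "will be performed on genomic DNA isolated from control and group blood samples and will be compared".

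For the translocation assay the same section says: "Assessment of chromosomal translocations: (pre and post intervention) Genomic DNA will be extracted from WBCs isolated". DNA from both visits will therefore exist.

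The SAP does not mention telomere length. Section 6.1 gives a t-test, "paired or unpaired as appropriate", or a rank-based equivalent. No baseline-adjusted comparison of the arms is named for any outcome.

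**The concern.** The Time Line is the list a laboratory would work from. A team that follows it, together with the telomere entry, could run one qPCR per guard, compare the two arms, and believe it had done what was asked. Two things would then be lost.

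- **The before/after result.** Objective 1 asks for change in the markers. One value per guard cannot describe change within an arm.
- **Precision.** Guards aged 20 to 60 will differ in telomere length for reasons unrelated to three months of yoga. A day-0 value used as covariate removes the part of that spread which persists from visit to visit. Without it, the whole spread stays in the standard error.

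A baseline value also has a practical use here. Exclusion criterion iv removes non-compliers from the yoga arm only, and SAP section 7 specifies complete-case analysis, so the guards analysed may not be the full randomised set. Day-0 values would show whether those who remain differ, and allow adjustment. SAP section 3 also defines the Full Analysis Set by having baseline and outcome data, which is unclear for an outcome with no scheduled baseline.

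**Working it through.** **Coverage of the schedule.** The Time Line has eight rows: four tests at two visits. The tests are cortisol, DDR (immunofluorescence with gene expression), "Nested PCR for Chromosomal Translocations", and the comet assay. Checking the laboratory outcomes in the Variables list against it:

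| Outcome | Pre/post label | Time Line rows |
|---|---|---|
| Cortisol | yes | 0 day, 3 months |
| Translocations | yes | 0 day, 3 months |
| Immunofluorescence | no | 0 day, 3 months |
| Gene expression | no | 0 day, 3 months |
| Comet assay | no | 0 day, 3 months |
| Telomere length | no | none |

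**The plan's own figures.** No sample size is given for telomere length. For the trial as a whole, 206 / 0.9 = 228.9, which rounds up to the stated 229. The 206 itself cannot be checked, because the pilot's variability is not given. With the precision formula n = (z/r)² × CV², z = 2.58 and r = 0.2, n = 166.41 × CV², so 206 would need a CV of about 1.11. Below, 206 serves only as the number of completers.

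**Inputs for precision.**
- 103 per arm: 206 split equally (assumed; the readable text gives no allocation ratio).
- Two-sided 0.05 (SAP section 4).
- Power of 80% as a conventional reference, and 95% because the protocol's sample-size text uses it.
- Correlation ρ between day-0 and 3-month telomere length: not in the documents, so a range is shown.
- Effects in units of the between-person SD.

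**Unadjusted comparison of 3-month values.** SE = SD × √(2/103) = 0.139 SD.
- 80% power: (1.96 + 0.84) × 0.139 ≈ 0.39 SD.
- 95% power: (1.96 + 1.645) × 0.139 ≈ 0.50 SD.

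**ANCOVA with the day-0 value.** The SE is multiplied by √(1 − ρ²). The equivalent gain in sample size is 1/(1 − ρ²).

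| ρ (assumed) | √(1 − ρ²) | Detectable, 80% power | Detectable, 95% power | Sample-size equivalent |
|---|---|---|---|---|
| 0.6 | 0.80 | 0.31 SD | 0.40 SD | 1.6 times |
| 0.8 | 0.60 | 0.23 SD | 0.30 SD | 2.8 times |
| 0.9 | 0.44 | 0.17 SD | 0.22 SD | 5.3 times |

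**Power for a true difference of 0.2 SD.** Unadjusted: 30%. ANCOVA: 38%, 52% or 91% at ρ = 0.5, 0.7 or 0.9.

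**The case against.** The strongest reply is that the Design section already settles the timing: dependent variables are assessed before and after, and telomere length is listed under Variables. On that view the missing rows are a clerical slip. Much of this stands. A reader might infer that telomere length has no before/after visit, or that a one-visit cross-sectional comparison was chosen. The documents do not support that: the general rule says otherwise, the telomere entry never says one visit, and other assays also lack the pre/post label. The Work plan figure and Flow Chart 3 are not readable here and might place the assay. What remains is that the readable operational list omits it.

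Three further inferences go too far.
- **That a yoga effect could not be told apart from differences at randomisation.** A 3-month comparison of intact randomised arms is unbiased, and chance imbalance is already in its standard error. The issue is precision.
- **That a single-visit comparison is the least precise possible.** A plain change score has variance factor 2(1 − ρ) and is worse whenever ρ is below 0.5. At ρ = 0.3 it detects 0.46 SD at 80% power, against 0.39 SD.
- **That this is the only laboratory measure without a visit.** That is true of the Variables list. The Introduction also promises a measure that has no visit anywhere: "We will also estimate the extent of oxidative free radicals as well as other DNA repair machinery".

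It is also fair to say that adding rows alone gains nothing between arms. The gain needs the adjusted analysis, which the SAP gives for no outcome. The other markers do have scheduled day-0 values, so adjustment remains open to them. For telomere length even the measurement is not clearly scheduled. Finally, the marker is named in neither the Objectives nor the SAP, so nothing suggests that it is a key endpoint.

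**Conclusion.** The point holds as an inconsistency with a cheap improvement attached. The Design section implies telomere length at both visits. The Time Line omits it, and the only stated analysis is a control-versus-group comparison, to which the SAP adds only unadjusted tests. A before/after result for this marker is therefore not secured.

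The possible loss is one of precision, not validity, and arises if the arms are compared without the day-0 value. At 80% power it is the gap between about 0.39 SD and 0.31 to 0.17 SD. This rests on 103 completers per arm and on a correlation between 0.6 and 0.9, neither of which the documents state. A lower correlation would shrink the gain. The consequence is confined to one outcome.

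**What to change.** 1. Add telomere length to the Time Line at 0 day and 3 months, using the genomic DNA already extracted at both visits for the translocation PCR.
2. Add one sentence to the SAP: arms are compared on 3-month telomere length adjusted for the 0-day value (ANCOVA), with the effect estimate and 95% confidence interval. This replaces the unadjusted control-versus-group comparison.
3. If a single measurement is intended after all, say at which visit and why, and exempt this marker from the before/after statement in the Design section.

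Running each guard's two samples on the same qPCR plate is an optional refinement. The cost is two table rows, one analysis sentence and at most one more qPCR per guard, with no extra blood draw or visit.

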## **Intervention: Specific Yoga module designed for proposed work**

## 'Practice Time

\*Transition Time

This module was designed and validated for stress among Antarctic expeditioners (Balakrishnan et al., 2019). The classical Yoga texts does not specify symptom based guidelines to practice Yoga, because the primary objective of Yoga is to gain mastery over mind. The observed physical and mental benefits are by-products of yoga practice. Therefore, the practices included in this module were selected from the ancient texts based on their approximating descriptions of mental and physical health benefits and the feasibility of practice by commoners. This Yoga module was validated by 30 experts who agreed to most of the practices and the final module was used as an intervention in the 35th Indian Scientific Expedition to Antarctica.

**Total duration in weeks/months for yoga therapy: 3 months (13 Weeks: 5 days a week)**

### **Time schedule of activities giving milestones**

#### First year:

- A. Recruit policemen and get them to fill a questionnaire in order to identify most stressed individuals.
- B. Obtain blood samples, isolate PBMCs, serum and plasma. Biochemical analysis to test for cortisol levels will be performed.
- C. The subjects will be given yoga training for 3 months along with studying DNA damage response and repair using comet assay, immunofluorescence and real-time PCR.
- D. Follow up of the subjects to ensure compliance for yoga protocol.

#### Second year:

- A. Continue with isolation of plasma, serum and PBMCs for studying DDR and DNA repair for the next group.
- B. Analysis of data from the first year will be performed

Third year:

Compiling of data, interpretation and analysis.

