### Methodology

Recruitment of individuals: Department of Police, Chandigarh has agreed to help us on this aspect. Policemen working for Chandigarh Police will be chosen based on the inclusion and exclusion criteria.

Subjects: Those security guards (age: >20 and <60) who are willing to consent to participate in this study will be screened for moderate and higher stress on Cohen's PSS, according to inclusion criteria and randomly divided between Intervention (Yoga Group) and Control Group.

Sample Size: The sample size of 206 was calculated for 99% confidence level (reliability coefficient = 2.58), at the alpha level of 0.05, a power of 0.95, and a relative precision of 0.2, derived from a pilot study done on breast cancer patients and yoga practitioners (Ram et al, 2013). Assuming a 10% drop out rate, a total of 229 subjects will be recruited.

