6.2 Comparisons of More Than Two Groups

- **Normally distributed data:** One-way ANOVA.
 - **Post hoc:** Dunnett's multiple comparisons test (for comparison against a control group).
- **Non-normal data:** Kruskal-Wallis test.
 - **Post hoc:** Dunn's multiple comparisons test.

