6.3 Correlation Analyses

- **Normally distributed data:** Pearson's correlation coefficient.
- **Non-normal data:** Spearman's rank correlation coefficient.

7. Handling of Missing Data

- Data will be analyzed as observed (complete case analysis).
- No imputation will be performed unless otherwise specified in the protocol.

8. Interim and Sensitivity Analyses

- No interim analyses are planned.
- Sensitivity analyses may be conducted to confirm robustness of results (e.g., excluding participants with protocol deviations).

9. Reporting

- Results will be presented in accordance with **CONSORT/CONSORT-Extension guidelines**.
- Statistical outputs will include effect sizes, 95% confidence intervals, and exact p-values.

Principal Investigator

[name]

Additional Professor

Department of Experimental Medicine and Biotechnology

PGIMER, Chandigarh

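### The schedule implies successive groups of guards, but no between-arm test in the SAP has a group or batch term, which would cost precision in unpaired comparisons of post-intervention values

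*Protocol*

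**What the plan says.** **Protocol, Time schedule of activities.** The first year begins with "Recruit policemen and get them to fill a questionnaire in order to identify most stressed individuals". Blood sampling, three months of yoga training and the DNA damage assays follow in the same year. The second year has two items: "Continue with isolation of plasma, serum and PBMCs for studying DDR and DNA repair for the next group", and "Analysis of data from the first year will be performed". No second round of recruitment or training is listed.

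**Protocol, Methodology.** Eligible guards are to be "randomly divided between Intervention (Yoga Group) and Control Group". The visible text gives no ratio and no blocking or stratification by group or year. The protocol's Variables section has outcomes measured before and after the intervention, with WBCs and plasma stored at -80°C. It does not say that a guard's two samples are assayed together.

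**SAP 6.1 and 6.2.** For two groups the tests are "Student's *t*-test (paired or unpaired as appropriate") or, for non-normal data, "Wilcoxon matched-pairs signed rank test (paired) or Mann-Whitney test (independent"). For more than two groups they are one-way ANOVA or the "Kruskal-Wallis test". All are single-factor or two-sample procedures, and none is stratified. Section 8 makes sensitivity analysis optional, and its only example is leaving out guards with protocol deviations.

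**The concern.** When laboratory work is spread over years, measured levels can move with reagent lots, operators, season or duty load. Comet scores, immunofluorescence counts and qPCR results could all shift in this way. If the analysis ignores the group a guard belongs to, the shift is counted as unexplained variation between guards. A real yoga effect is then harder to see.

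The SAP does not say that groups will be pooled; that follows from the lack of any group term. Nor does it commit the arm comparison to change scores. Its choice between paired and unpaired tests is left open, so an unpaired comparison of post-intervention values is allowed, and that is the exposed one.

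**Working it through.** **Inputs from the documents.** Sample size before dropout is 206 and total recruited is 229 (Protocol, Methodology). Alpha is 0.05, two-sided (SAP section 4). The dropout step reproduces: 206 / 0.90 = 228.9, rounded up to 229. The 206 itself cannot be rebuilt because the pilot mean and SD, or rate, are not given. It is used here only as the number analysed.

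**Assumptions.** 1:1 allocation (103 per arm), two groups of equal size, a level shift *s* between groups of 0.5 to 1.0 within-group SD, and a yoga effect of 0.4 SD. None of these is in the documents.

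**Step 1: variance and power.** With a share *f* of guards in the first group, the pooled variance in within-group SD units is v = 1 + f(1 − f)s². At f = 0.5 this is 1 + s²/4. Effective N is 206 / v. The noncentrality of the unpaired t-test is 0.4 / √(2v/103), on 204 degrees of freedom.

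| Shift s (SD) | v | Effective N | Noncentrality | Power for 0.4 SD |
|---|---|---|---|---|
| 0 | 1.00 | 206 | 2.87 | 0.815 |
| 0.5 | 1.06 | 194 | 2.78 | 0.79 |
| 0.75 | 1.14 | 181 | 2.69 | 0.76 |
| 1.0 | 1.25 | 165 | 2.57 | 0.72 |

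For an assumed 0.5 SD effect (normal approximation), power is 94.8% with a group term. Without it, power is 93.6% at a 0.5 SD shift and 89.4% at 1.0 SD. At 1.0 SD, about 206 × 1.25 = 258 guards would be needed to recover the loss.

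**Step 2: paired tests and change scores.** If both samples of a guard carry the same shift, (post + s) − (pre + s) = post − pre, and the shift drops out. The three-month intervention allows both samples to fall in the same group. In simulation (5,000 trials per case, 206 guards, half the within-group variance shared by a guard's two samples), the arm comparison of change without a group term held a type I error of 4.6% to 5.3% in every case.

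**Step 3: bias and type I error of the unpaired post-value t-test (nominal 5%).** The expected bias is s times the difference between the arms in their share of guards from the second group.

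| Allocation over groups | Shift 0.5 SD | Shift 1.0 SD | Mean bias |
|---|---|---|---|
| Randomised across all guards | 4.8% | 4.4% | about 0 |
| Balanced within each group | 4.3% | 2.8% | about 0 |
| Fixed 60/40 versus 40/60 | 10.4% | 23.1% | 0.10 and 0.21 SD |

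With a group term, type I error was about 5% in all six cases (4.7% to 5.0%).

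**Step 4: how likely is the third row by chance?** The SD of the chance difference in group share between arms is √(2 × 0.25 / 103) = 0.070. A 60/40 versus 40/60 split is a difference of 0.20, which is 0.20 / 0.070 = 2.9 SD, with a two-sided probability of about 0.4%.

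**The case against.** The strongest reply is that randomisation already protects the arm contrast. A reader might infer from the yearly groups that the treatment effect is biased or the false-positive rate inflated. The documents do not support this. Allocation is stated to be random, so expected bias is zero. Chance imbalance over groups is already covered by the test's standard error, and type I error stays at or below about 5%. The 10% figure needs the arm mix to differ systematically between groups, and no passage shows that. This part of the objection stands.

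A reader might also infer that every planned test suffers. That is too broad, as Step 2 shows. One reservation remains: the cancellation needs a guard's two samples to share the shift, and nothing in the visible text requires them to be processed together.

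Third, the facts are thin. Recruitment and training appear only under the first year, so the next group could be a laboratory batch rather than a second intake. The work plan figure and the allocation flow chart cannot be seen and may describe allocation. No document gives the size of any shift, and at 0.5 SD the power loss is about two percentage points. All of this is fair and limits the weight of the point. It does not remove it: under either reading of the phrase, the laboratory work is divided over time and the between-arm tests make no allowance for that.

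**Conclusion.** The point holds as a modest one about precision. The schedule implies at least two successive groups, and SAP 6.1 and 6.2 contain no group or batch term. The exposed analysis is the unpaired between-arm comparison of post-intervention values. There the loss is small at a shift of 0.5 SD and material near 1.0 SD, where variance rises by 25% and power for a 0.4 SD effect falls from 0.815 to 0.72. These sizes rest on the assumed shifts, effect, equal halves and 1:1 allocation.

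Bias remains conditional. It would arise only if the arm mix differed systematically between groups; a 60/40 versus 40/60 split with a 0.5 SD shift would give 0.2 × 0.5 = 0.10 SD of bias and about 10% type I error. The visible text neither shows nor rules out such a difference, because it does not describe allocation within groups.

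**What to change.** 1. State in the protocol how many recruitment groups there are, their planned size, and whether randomisation is done within each. Where allocation is still to come, allocate in equal numbers to the two arms within each group.
2. In the SAP, include recruitment group as a fixed factor in every between-arm model, ideally with the baseline value as a covariate. Where a rank or binary test is kept, use the stratified version: van Elteren for ranks, Cochran-Mantel-Haenszel for a binary result such as translocation detected or not.
3. State whether a guard's two samples are assayed in the same batch. If batches do not match recruitment groups, say which of the two defines the stratum.

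Balance alone is not enough: with arms balanced within groups and a 1.0 SD shift, the test without a group term ran at 2.8% instead of 5%, so the term is needed as well. If allocation is already complete, the analysis term can still be specified.

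The cost is SAP wording and one degree of freedom per extra group, out of about 204. No extra guards, samples or visits are needed.

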Date: February 29, 2020

NCT number: Not

Available

Official Project Title

Investigating the Role of Yoga in Alleviating
Chromosomal Translocations in Security Guards
of Chandigarh Police Who Are Responsible for
the Safety of VIPs

Statistical Analysis Plan (SAP)

1. Introduction

This Statistical Analysis Plan (SAP) outlines the planned analyses for the study titled “Investigating the Role of Yoga in Alleviating Chromosomal Translocations in Security Guards of Chandigarh Police Who Are Responsible for the Safety of VIPs”. It defines the methods for analyzing study endpoints, including descriptive, inferential, and correlation analyses.

2. Objectives and Endpoints

1. Analysis of molecular markers related to DNA damage response and repair before and after the practice of yoga on Chandigarh Police.
2. To examine the molecular mechanism by which yoga may modulate DNA damage response and repair.

3. Analysis Populations

- **Full Analysis Set (FAS):** All participants meeting eligibility criteria and providing baseline and outcome data.
- **Per-Protocol Set (PPS):** Subset of participants completing the study without major protocol deviations.

4. General Statistical Considerations

- All analyses will be conducted using **GraphPad Prism v8.0.2** and **JASP v0.19.3**.
- Two-sided significance level of $\alpha = 0.05$ will be applied.

- Adjusted p-values from post hoc tests will also use the **0.05 threshold** for significance.
- Continuous variables will be summarized with **mean \pm SD** (if normally distributed) or **median with interquartile range** (if non-normal).
- Categorical variables will be summarized as **frequencies and percentages**.

5. Assessment of Assumptions

- **Normality:** Assessed using the **Shapiro-Wilk test**.
- **Homogeneity of variance (ANOVA assumption):** Checked using **Levene's test**.

6. Statistical Methods

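### Does the second-year analysis of first-year data amount to an undeclared interim analysis, contrary to SAP section 8?

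*Protocol*

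**What the plan says.** The protocol's time schedule lists two activities for the second year. Item A is laboratory work: "Continue with isolation of plasma, serum and PBMCs for studying DDR and DNA repair for the next group". Item B reads: "Analysis of data from the first year will be performed". The third year has one line: "Compiling of data, interpretation and analysis".

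SAP section 8 states: "No interim analyses are planned". SAP section 4 sets a single error level, with no division across looks: "Two-sided significance level of $\alpha = 0.05$ will be applied". SAP section 6.1 provides for both pre-post and between-arm t-tests ("paired or unpaired as appropriate").

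In the readable text, neither document says what the year-two work consists of, who sees it, or whether it involves any comparison. The work plan figure and the content of the allocation flow chart are not shown, so they cannot be consulted on this.

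**The concern.** Item B sits beside sample work for a group not yet finished, and a further analysis follows in year three. On its face that is analysis of accumulating data, which the SAP says will not happen.

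A comparison in year two would be feasible. The intervention lasts 3 months and assays are done at day 0 and 3 months, so people enrolled early in year one could have complete paired data by then. Laboratory work already has its own lines in the schedule (first year, items B and C; second year, item A), and item B speaks of data rather than samples. That makes it less obvious that bench work is meant.

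The false-positive rate would be at stake. Testing an endpoint at 0.05 on first-year data and again at 0.05 on all data, with the option to claim either result, gives more than 5% error for that endpoint. A reader who took item B as a planned look would find no alpha split and no restriction on access.

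**Working it through.** **Is a comparison planned?** The plan attaches no number to this point. The totals of 206 (before dropout) and 229 (recruited) are not split by year. The question is first one of wording.

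- Item B names no arm, contrast, endpoint, test, decision or stopping rule.
- The protocol often uses the word analysis for laboratory work. First year, item B: "Biochemical analysis to test for cortisol levels will be performed". Variables: "Isolated PBMCs will be subjected to DDR analysis by immunofluorescence".
- The second year lists no separate step for reading out, checking or cleaning first-year results, although with sampling spread over more than one year that work has to be done somewhere.
- Interpretation appears only in the third-year line, after compiling. That fits a single inferential analysis at the end.
- SAP section 8 is the only text that addresses interim analyses, and it excludes them.

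Item B is therefore compatible with section 8. The wording does not prove this reading, but nothing in it establishes the other.

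**What would a comparative look cost?** Inputs: two-sided 0.05, critical value 1.96 (SAP section 4). The share f of the final information available from year one is not stated, so it is an assumption and is varied.

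Under the null hypothesis, the statistics Z1 (first-year data) and Z2 (all data) are bivariate normal with correlation √f. The chance that at least one is significant is

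P(|Z1| > 1.96 or |Z2| > 1.96) = 0.05 + 0.05 − P(both significant).

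| f (assumed) | Correlation √f | P(both) | P(either) |
|---|---|---|---|
| 0.10 | 0.316 | 0.0051 | 0.0949 |
| 1/3 | 0.577 | 0.0117 | 0.0883 |
| 1/2 | 0.707 | 0.0169 | 0.0831 |
| 2/3 | 0.816 | 0.0230 | 0.0770 |
| 0.90 | 0.949 | 0.0352 | 0.0648 |

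At f = 1/2 the excess over the nominal level is 0.0831 − 0.05 = 0.0331. At that f, an equal nominal level of about 0.029 at each look would bring the total back to 0.05.

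**When does the excess arise?** Three things must all be true: the year-two work compares arms or time points, it is tested at 0.05, and a positive result at either look may be claimed. If any one fails, the error rate is that of the final test, 0.05. The documents state none of the three for the year-two work.

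**A variant that does not count.** Suppose the further group were the control arm, so that year two allowed only a pre-post test within the yoga arm, followed by a between-arm test of change at the end. With no mean change in either arm, equal variances and a yoga share q of the sample, the two statistics correlate at √(1 − q). For q = 1/2 that is 0.707, and the chance that either is significant is again 0.0831. But the pre-post test would use the complete yoga arm whenever it was run, so the 8.3% is the same if both tests are run once, after the last sample. It is the price of testing two hypotheses, not of looking early. The premise is also doubtful: the Subjects and Design of the study sections describe eligible guards randomised to both groups and assessed before and after the intervention period.

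**The case for a change.** The strongest argument for acting is that a plan should not need a charitable reading. Item B is written as analysis of data, separately from the bench-work lines, and in the third-year line the same word stands beside compiling and interpretation, which are not laboratory tasks. Readers cannot tell from the text which sense governs, and one of the two contradicts the SAP. The first-year data could support a comparison, nothing readable restricts access, and one clarifying line would settle the matter at almost no cost.

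Much of this stands. The line is ambiguous, the two documents are not cross-referenced, and the 8.3% is correct under its conditions. What does not follow is that the plan permits an interim test. An ambiguous calendar entry does not override an explicit statement in the document that governs the analysis, and where one reading agrees with that statement, an analyst would take it. A clarifying line would do no harm, but it would alter no analysis that the SAP specifies. A ban on any comparison before database lock would go further than needed, since neither document mentions a lock.

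**Conclusion.** The concern does not call for a change. Item B is loosely worded beside SAP section 8, but it is a milestone entry with a natural reading that agrees with the SAP: getting first-year results read out, checked and described while later samples are processed. Under that reading, with each endpoint's test run once on the full data at two-sided 0.05, the type I error of that test is 5%, with or without a rewording.

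The figure of about 8.3% (9.5% to 6.5% for year-one shares of 10% to 90%) describes a different conduct of the trial: a comparative look, at 0.05, with a claim allowed at either time. The year-one share is assumed, and the readable text supports none of those conditions. The conclusion rests on the team following SAP section 8 as written, and on the figures that are not shown containing nothing to the contrary. If a comparative look was in fact carried out, the excess above would apply, and the fault would be a departure from the SAP rather than a defect in it.
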